1. PREVIOUS STUDY HISTORY

Has this study ever been reviewed and rejected/disapproved by another IRB prior to submission to this IRB?

No Yes – if yes, please explain: |

2. BRIEF SUMMARY OF RESEARCH

- *The summary should be written in language intelligible to a moderately educated, non-scientific layperson.*
- *It should contain a clear statement of the rationale and hypothesis of your study, a concise description of the methodology, with an emphasis on what will happen to the subjects, and a discussion of the results.*
- *This section should be ½ page*

Rationale: COVID-19 is associated with a marked inflammatory response, resulting in both systemic and pulmonary damage – the most devastating being Acute Respiratory Distress Syndrome (ARDS), which often results in invasive mechanical ventilation and higher mortality. Treatment for COVID-19 patients with respiratory failure has been vexing, but the use of steroids, which can help attenuate both the inflammatory and fibrotic process of lung injury, has shown promise. In a recent randomized control trial, dexamethasone 6 mg once daily showed a modest decrease in mortality among hospitalized COVID-19 patients with respiratory failure, which has been defined as patients who require oxygen supplementation or invasive mechanical ventilation. Thus, dexamethasone 6mg daily is being routinely used to treat COVID-19 patients.

Other trials have shown that the inflammatory response to COVID-19 can be further attenuated at higher dosages of dexamethasone. These higher dosages have not been well studied and have not been directly compared to the current standard dose of dexamethasone 6 mg daily. We propose that a higher dexamethasone dose, equivalent to methylprednisolone 1 mg/kg/day which is routinely used to treat other inflammatory conditions of the lungs, may be more effective than the current standard dose in reducing mortality in COVID-19 patients with respiratory failure.

Methodology: We will include hospitalized adult patients with COVID-19 infection with hypoxemia requiring oxygen supplementation. Eligible patients will be randomized in a 1:1 fashion to receive either standard dose of dexamethasone at 6 mg daily, or higher, weight-based dose of dexamethasone at 0.2 mg/kg/day (which is equivalent to methylprednisolone 1 mg/kg/day).

Outcomes: The primary outcome will be all-cause mortality at 28 days. The secondary outcomes will include need for ICU admission, ICU length of stay,

hospital length of stay, higher requirements of oxygen supplementation (e.g. venturi mask, non-rebreather mask, high-flow nasal cannula or non-invasive mechanical ventilation), invasive mechanical ventilation, duration of mechanical ventilation, tracheostomy, ECMO, subjective symptoms at 28 days, disposition upon discharge, oxygen supplementation upon discharge, development of secondary bacterial or fungal infections and development of clinically significant hyperglycemia.

3. INTRODUCTION/BACKGROUND MATERIAL/PRELIMINARY STUDIES AND SIGNIFICANCE

- *Describe and provide the results of previous work by yourself or others, including animal studies, laboratory studies, pilot studies, pre-clinical and/or clinical studies involving the compound or device to be studied.*
- *Include information as to why you are conducting the study and how the study differs from what has been previously researched, including what the knowledge gaps are.*
- *Describe the importance of the knowledge expected to result*

The use of steroids in COVID-19 infection was initially controversial and was not recommended early in the pandemic. Later, observational, retrospective studies suggested a role for steroids in COVID-19. A subsequent randomized clinical trial (RECOVERY) showed clinical benefit with steroids. In particular, the study showed that the use of dexamethasone 6 mg once daily was associated with a decrease in mortality in COVID-19 patients requiring oxygen supplementation, particularly in those requiring invasive mechanical ventilation. However there was no benefit in those patients, who did not require oxygen supplementation. Since the findings were reported, the use of dexamethasone 6 mg once daily for 10 days in COVID-19 patients with respiratory failure has been routinely used in clinical practice. Other studies, however, suggest that a higher dose of dexamethasone may be beneficial. The CoDEX trial, a multicenter, randomized clinical trial conducted in Brazil, studied the effects of dexamethasone in patients with COVID-19 in moderate to severe ARDS requiring mechanical ventilation. Ultimately, the investigators found that the use of dexamethasone at a dose of 20 mg daily for 5 days followed by 10 mg daily for an additional 5 days was associated with an increase in ventilator-free days compared to supportive care alone. Another randomized, single-blinded control trial using 250 mg of intravenous methylprednisolone showed a significant decrease in mortality rate when compared to patients who did not receive steroids. The ideal dose of dexamethasone remains unclear, and to the best of our knowledge, there are no studies at this time comparing different doses of dexamethasone in this population.

4. OBJECTIVE(S)/SPECIFIC AIMS AND HYPOTHESES

- *A concise statement of the goal(s) of the current study.*
- *The rationale for and specific objectives of the study.*
- *The goals and the hypothesis to be tested should be stated.*

The aim of the study is to compare the efficacy of dexamethasone at the current recommended dose versus a higher, weight-based dose. We hypothesize that the use of a higher, weight-based dose of dexamethasone equivalent to 1 mg/kg/day of methylprednisolone would be associated with a decrease in mortality in COVID-19 patients requiring oxygen supplementation.

Primary outcome:

- All-cause mortality at 28 days

Secondary outcomes:

- ICU admission
- ICU length of stay
- Hospital length of stay
- Need for higher oxygen supplementation including venturi mask, non-rebreather mask, high flow nasal cannula or non-invasive mechanical ventilation
- Invasive mechanical ventilation
- Duration of invasive mechanical ventilation
- ECMO
- Need for tracheostomy
- Development of secondary bacterial or fungal infections
- Development of clinically significant hyperglycemia, which will be defined as need for insulin drip or ICU admission to control hyperglycemia
- Oxygen supplementation upon discharge from the hospital
- Subjective symptoms at 28 days
- Disposition upon discharge (home, home with physical therapy, skilled nursing facility, long-term acute care facility, long-term care facility / nursing home, acute rehabilitation facility, hospice care, death)

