10. ENDPOINTS

- *Describe the primary and secondary study endpoints*
- *Describe any primary or secondary safety endpoints*

Primary study endpoint: all-cause mortality at 28 days.

Secondary study endpoints: need for ICU admission, ICU length of stay, hospital length of stay, higher requirements of oxygen supplementation (venturi mask, non-rebreather mask, high-flow nasal cannula or non-invasive mechanical ventilation), invasive mechanical ventilation, duration of invasive mechanical ventilation, ECMO, tracheostomy, subjective symptoms at 28 days, disposition upon discharge, and oxygen supplementation upon discharge.

The primary and secondary safety endpoints will include the development of secondary bacterial or fungal infections that is objectively identified based on culture data, and clinically significant hyperglycemia requiring ICU stay or insulin drip.

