12. STATISTICAL ANALYSIS

- *Describe how your data will be used to test the hypotheses.*
- *State clearly what variables will be tested and what statistical tests will be used.*
- *Include sample size calculations.*

- *If this is a pilot study, state which variables will be examined for hypothesis generation in later studies.*

In general, baseline patient characteristics including demographics and clinical data will be summarized using descriptive statistics for all data combined and data by treatment arm. Specifically, continuous variables will be summarized using mean, standard deviation and median; categorical variables will be summarized using frequencies and percentage. No inferential comparison of treatment arms will be made with respect to baseline and demographic clinical data; such comparisons will be descriptive only. Unless otherwise specified, all results will be considered significant if $p < 0.05$. All data analysis will be performed using SAS 9.4 (SAS institute Inc., Cary, NC). The intent-to-treat (ITT) principle will be employed, i.e all randomized patients in the groups to which they are randomly assigned will be included in the final analysis, regardless of the intervention they actually receive, and regardless of withdrawal from treatment or deviation from the protocol for any reason.

The primary endpoint is all-cause mortality at 28 days. It will be compared between the two treatment arms using chi-squared test or Fisher's exact test.

Among the secondary study endpoints, binary variables (need for ICU admission, need for higher oxygen supplementation including non-rebreather mask, high flow nasal cannula or non-invasive mechanical ventilation, need for invasive mechanical ventilation and need for oxygen supplementation upon discharge) will be compared using chi-squared test or Fisher's exact test between the two arms; continuous variables (ICU length of stay, hospital length of stay, duration of mechanical ventilation) will be compared between the two arms using Kaplan-Meier curve and log-ran test to take into account data censoring.

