Sample size consideration: The sample size calculation was based on the hypothesis of primary endpoint. Our primary hypothesis is that the use of a higher dose of dexamethasone equivalent to 1 mg/kg/day of methylprednisolone would be associated with a decrease in mortality in COVID-19 patients requiring oxygen supplementation. A two group χ^2 test with a 5% two-sided significance level will have 80% power to detect the difference between the proportion of dexamethasone 6 mg group 23.3% and the proportion of dexamethasone weight based 5.9% (odds ratio of 0.206) when the sample size in each group is 64.

To account for 10% dropout rate, will be increasing recruitment to 142, with 71 in each arm to ensure 128 evaluable subjects.

Missing data: If there is less than 5% of an endpoint missing, complete case analysis will be used; if there is more than 5% missing, sensitivity analysis will be performed by assuming all the missing values of an endpoint to be either outcome if it is binary, or by assuming all the missing values of an endpoint to be either upper quartile or lower quartile of the available values if it is continuous, to see if the results are similar to those using complete case analysis.

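### Neither the higher-oxygen endpoint nor the invasive-ventilation endpoint has a rule for death, and the listed oxygen devices end at non-invasive ventilation

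*Combined protocol and SAP*

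**What the plan says.** The oxygen endpoint is described several times, and not in the same way.

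- Section 2 (Brief Summary) has an open list: "higher requirements of oxygen supplementation (e.g. venturi mask, non-rebreather mask, high-flow nasal cannula or non-invasive mechanical ventilation), invasive mechanical ventilation".
- Section 4 (Objectives) also has an open list: "Need for higher oxygen supplementation including venturi mask, non-rebreather mask, high flow nasal cannula or non-invasive mechanical ventilation".
- Section 10 (Endpoints) has a closed list in brackets: "higher requirements of oxygen supplementation (venturi mask, non-rebreather mask, high-flow nasal cannula or non-invasive mechanical ventilation), invasive mechanical ventilation". The data-collection list in Section 11 is closed in the same way.
- Section 12 (Statistical Analysis) is open again but leaves out the venturi mask: "need for higher oxygen supplementation including non-rebreather mask, high flow nasal cannula or non-invasive mechanical ventilation, need for invasive mechanical ventilation".

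Invasive ventilation is a separate item everywhere. ECMO is a separate secondary endpoint in Sections 4 and 10, but Section 12 does not name it among the binary variables to be tested.

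For the binary secondary endpoints, Section 12 says that they "will be compared using chi-squared test or Fisher's exact test between the two arms". The analysis set is intention-to-treat: "all randomized patients in the groups to which they are randomly assigned will be included in the final analysis". The missing-data rule begins "If there is less than 5% of an endpoint missing, complete case analysis will be used" and does not mention death. Death appears only as the primary endpoint and as a category of discharge disposition.

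**The concern.** A binary variable for needing a given level of support has a natural default: no record of the device means no event. Patients who die stay in the denominator. A patient who dies on low-flow oxygen therefore has a complete record reading 'no' on both endpoints. That is not a missing value, so the missing-data rule does not apply. Likewise, a patient who goes from nasal cannula straight to intubation has used none of the devices on the closed list.

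A death then counts the same as an uneventful recovery on these two endpoints. If one arm has fewer deaths, part of its advantage is removed from the escalation comparison. If the higher dose raised mortality, part of that harm would be hidden in the same way. These endpoints describe the respiratory course alongside the mortality result, so a reader needs to know what a non-event means.

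**Working it through.** **1. The plan's own figure.** Inputs from Section 12: 23.3% v 5.9%, two-sided 5%, 80% power. With the pooled-variance formula and mean proportion 0.146:

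n = [1.96 × √(2 × 0.146 × 0.854) + 0.8416 × √(0.233 × 0.767 + 0.059 × 0.941)]² / 0.174² = (0.979 + 0.407)² / 0.0303 ≈ 63.5, so 64 per arm.

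Power at 64 per arm is 80.3%. The stated figure reproduces. It concerns mortality only; no calculation is given for the two secondary endpoints.

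**2. The definitions side by side.**

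| Section | How the list opens | Venturi mask | Invasive ventilation |
|---|---|---|---|
| 2 | 'e.g.' | yes | separate |
| 4 | 'including' | yes | separate |
| 10 | closed | yes | separate |
| 11 (data list) | closed | yes | separate |
| 12 | 'including' | no | separate |

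No row says whether intubation or ECMO counts as higher oxygen support, and none mentions death.

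**3. Default scoring.**

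| Course | Oxygen endpoint (closed list) | Invasive ventilation |
|---|---|---|
| Intubated directly from nasal cannula | no event | event |
| Dies with no escalation | no event | no event |

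**4. Size of the death component.** Expected deaths with 71 per arm: 71 × 0.233 = 16.5 and 71 × 0.059 = 4.2. Let f be the share of deaths that had no event on the endpoint. The documents give no value for f, so it is assumed, and taken as equal in both arms. Deaths scored as non-events number 71 × p × f. Counting them as events moves the risk difference by f × (23.3 − 5.9) = 17.4f percentage points.

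| f (assumed) | 6 mg arm, per 71 | Higher-dose arm, per 71 | Shift (points) |
|---|---|---|---|
| 10% | 1.7 | 0.4 | 1.7 |
| 25% | 4.1 | 1.0 | 4.4 |
| 50% | 8.3 | 2.1 | 8.7 |

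The share need not be the same for the two endpoints: a patient who dies on non-invasive ventilation is an event on the oxygen endpoint but not on the ventilation endpoint.

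**5. Illustration.** Assume 20% are intubated in each arm, so the ventilation endpoint alone shows a difference of 0. With f = 25%, ventilation or death is 20 + 5.8 = 25.8% v 20 + 1.5 = 21.5%, a difference of about 4.4 points.

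Directly intubated survivors are not in these figures. The documents give no basis for their number or their split between arms.

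**The case against.** A reader might infer that the plan scores direct intubations and deaths as successes. It does not say so. The scoring is undefined, the data form is not in the documents, and the open wording in Sections 2, 4 and 12 allows intubation to count as higher support. That stands. What remains is that Section 10, the section that sets the endpoints, has a closed list, and that seven hospitals (Section 6) could read the wording differently.

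A reader might also infer that these outcomes are lost. They are not: a direct intubation is an event on the ventilation endpoint, and every death by day 28 is an event on the primary endpoint. Only the death gap affects both secondary endpoints.

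A third inference is that the bias could reverse the comparison. Nothing in the documents shows that. The size rests on an assumed share, and excluding DNR/DNI patients at entry (Section 7) should limit deaths without intubation, although code status can change later. With equal mortality, and the same share in each arm, no differential shift from deaths is expected.

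Finally, separate component endpoints are a legitimate choice, and an explicit rule for death would also close the gap. Composites with death take in the primary endpoint's events. Both points are fair; the second is the price of the proposed fix.

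**Conclusion.** The concern holds as a gap in the definition of two secondary endpoints. No rule covers death on either endpoint, and the device lists disagree on whether they are closed and whether they include the venturi mask. Under default coding, and if mortality differs as the sample size assumes, both endpoints are biased against the arm with fewer deaths, by about 2 to 9 percentage points for assumed shares of 10% to 50%. That range rests on the planned mortality rates, an equal share in both arms, and default 'no event' coding. The true share cannot be found from the documents. The documents do not support saying that these patients are already coded as successes, or that the result would reverse. The primary analysis and the 64 per arm are untouched.

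**What to change.** In Sections 2, 4, 10 and 12, and in the Section 11 data list, use one reconciled device list and define:

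- (a) *escalation above baseline support to any listed device, invasive ventilation or ECMO during the index hospitalisation up to day 28, or death by day 28*;
- (b) *invasive ventilation or ECMO during the index hospitalisation up to day 28, or death by day 28*.

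State how patients already on a listed device, or already ventilated, at entry are counted, since Section 7 does not exclude them. Keep the single-component rates as descriptive rows.

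The support components need the hospitalisation limit. Section 9 ends participation at discharge or 28 days, whichever is first, and the post-discharge survey in Section 20 covers only the primary endpoint and symptoms.

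The cost is mainly wording: in-hospital support and 28-day deaths are already collected. Section 11 does not name support at entry, so one field may be needed; Section 20 already has investigators reviewing oxygen requirements at screening. The downside is that the composites share deaths with the primary endpoint and so are not independent support for it.

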11. RESEARCH PROCEDURES

- *Include a detailed description of all procedures to be performed on the research subject and the schedule for each procedure.*
- *Include any screening procedures for eligibility and/or baseline diagnostic tests*
- *Include procedures being performed to monitor subjects for safety or minimize risks*
- *Include information about drug washout periods*
- *If drugs or biologics are being administered provide information on dosing and route of administration*
- *Clearly indicate which procedures are only being conducted for research purposes.*
- *If any specimens will be used for this research, explain whether they are being collected specifically for research purposes.*
- *Describe any source records that will be used to collect data about subjects*
- *Indicate the data to be collected, including long term follow-up*

All hospitalized patients with COVID-19 infection documented by a positive PCR test who require oxygen supplementation or have documented hypoxemia based on oxygen saturation <94% will be screened for eligibility. Baseline diagnostics tests will be as per standard of care and no additional testing is required for our research purposes. All patients will receive routine medical care as per most updated COVID-19 guidelines prior to randomization.

Eligible patients who agree to participate in the study will be randomized 1:1 into two groups. Randomization was set up in REDCap. Once the patient gives consent, the randomization form on REDCap will randomize to either of the groups. As the study is multi-site, the randomization will be stratified by each site.

The standard dexamethasone group will receive a dose of 6 mg daily. The higher dexamethasone group will receive a dose of 0.2 mg/kg/day with maximum dose of 20 mg per day. The route of administration will be IV for both groups. No patients will receive less than dexamethasone 6 mg. The duration of treatment in both arms will be a total of 10 days of steroids or until discharge, whichever comes first.

No procedures, blood draws, imaging or diagnostic testing will be performed on the participants other than those indicated for their medical care.

Data will be obtained from the medical electronic records and tabulated in REDCap. Patient will be de-identified and REDCap access will be limited to appropriate investigators involved in the trial to avoid HIPAA violations.

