17. RISKS TO SUBJECTS

- *Describe any potential risks and discomforts to the subject (physical, psychological, social, legal, or other) and assess their likelihood and seriousness and whether side effects are reversible. Where appropriate, describe alternative treatments and procedures that might be advantageous to the subjects.*
- *Include risks to others, like sexual partners (if appropriate)*
- *Discuss why the risks to subjects are reasonable in relation to the anticipated benefits and in relation to the importance of the knowledge that may reasonably be expected to results*
- *Describe the procedures for protecting against or minimizing any potential risks, including risks to confidentiality, and assess their likely effectiveness.*

Potential risks for the patients in the higher dexamethasone dose group include but are not limited to higher risk of hyperglycemia, delirium and bacterial or fungal infections. Most of these side effects are treatable and reversible. To minimize any potential risks, patients will be monitored for signs or symptoms suggestive of secondary infections, so they can be identified and treated early. Glucose levels will be checked as part of routine medical care to ensure adequate control of hyperglycemia. For patients who develop delirium, use of non-pharmacological and pharmacological interventions will be offered based on clinical judgment. These risks are reasonable in relation to the potential benefits and importance of knowledge that can be obtained with the results of the study. A data and safety monitoring committee will be created to assess for the development of adverse events.

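### All-cause ICU admission overlaps with one criterion of the hyperglycemia safety endpoint, no reason for ICU admission is listed for collection, and the hyperglycemia endpoint rests on care decisions alone

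*Combined protocol and SAP*

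**What the plan says.** Sections 4 and 10 list ICU admission and ICU length of stay as secondary endpoints without restricting them by cause. Section 12 puts ICU admission among the "binary variables (need for ICU admission, need for higher oxygen supplementation" and others, to be compared by chi-squared or Fisher's exact test, and gives no analysis by reason for admission.

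Section 4 also lists the hyperglycemia outcome: "Development of clinically significant hyperglycemia, which will be defined as need for insulin drip or ICU admission to control hyperglycemia". Section 10 places it with the safety endpoints in slightly different words: "clinically significant hyperglycemia requiring ICU stay or insulin drip".

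Section 17 names hyperglycemia among the risks expected to be higher in the higher-dose group, and adds: "Glucose levels will be checked as part of routine medical care to ensure adequate control of hyperglycemia". Section 7 names diabetes as a common comorbidity. The data list in Section 11 includes ICU admission, length of ICU stay and clinically significant hyperglycemia, but neither the reason for ICU admission nor glucose values.

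**The concern.** A patient moved to the ICU only for glucose control enters three summaries: the hyperglycemia safety endpoint, ICU admission, and ICU length of stay. The protocol itself expects such events more often on the higher dose. They therefore act against any reduction in ICU admission from better control of the disease. If the ICU comparison came out flat, the report could not readily say whether the higher dose did nothing or whether a benefit was offset by a side effect. Those two conclusions mean different things to a reader choosing a dose.

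The second part concerns the safety endpoint itself. Both of its criteria, insulin drip and ICU admission, are decisions made by treating staff. No blinding is described, and Section 6 names seven recruiting hospitals whose practice may differ. Marked hyperglycemia managed on the ward by other means does not count, although glucose is measured routinely. Hyperglycemia is one of two named safety endpoints in Section 10 and one of the two side effects that the monitoring committee is to assess under Section 15, so an insensitive measure also weakens that oversight.

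**Working it through.** **1. The plan's own figure, and whether the overlap touches it.** Section 12 states: "A two group χ^2 test with a 5% two-sided significance level will have 80% power". Its inputs are 28-day mortality of 23.3% on 6 mg and 5.9% on the weight-based dose, and its result is 64 per arm. With p1 = 0.233, p2 = 0.059 and mean p = 0.146:

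n per arm = [1.960·√(2·0.146·0.854) + 0.842·√(0.233·0.767 + 0.059·0.941)]² / (0.233 − 0.059)²
= (0.979 + 0.407)² / 0.0303 = 63.5, rounded up to 64.

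Power at 64 per arm is 80.3%, and the odds ratio is (0.059/0.941)/(0.233/0.767) = 0.206. The figure reproduces. It concerns 28-day mortality, which does not depend on ICU admission, so the overlap leaves it unchanged.

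**2. Where the two endpoints overlap.**

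| Event | Hyperglycemia endpoint | ICU admission endpoint |
|---|---|---|
| Insulin drip, no ICU admission | Yes | No |
| ICU admission only to control glucose | Yes | Yes |
| ICU admission for another reason, no drip | No | Yes |
| ICU admission for another reason, drip given | Yes, through the drip | Yes |
| Marked hyperglycemia managed on the ward without a drip | No | No |

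The second and fourth rows give the same result on both endpoints. If the data form holds only one combined hyperglycemia indicator, these rows look alike, yet only in the second was the admission caused by glucose. The Section 10 wording, which speaks of an ICU stay rather than an admission to control glucose, leaves room for further variation in how cases are classified. The last row is missed by both endpoints.

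**3. Possible size, on assumed rates.** The documents give no ICU or hyperglycemia rates, so every rate here is an assumption. Let r be the proportion admitted to the ICU for other reasons, and h the proportion of the remaining patients admitted only for glucose control. Then all-cause ICU admission = r + (1 − r)·h. For example, with r = 15% and h = 3%: 0.15 + 0.85·0.03 = 17.55%. Power is for a two-sided 5% chi-squared test with 64 per arm.

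| r, 6 mg v higher | h, 6 mg v higher | All-cause ICU | Difference (points) | Power |
|---|---|---|---|---|
| 30% v 15% | 0 v 0 | 30.00% v 15.00% | 15.00 | 53% |
| 30% v 15% | 1% v 3% | 30.70% v 17.55% | 13.15 | 41% |
| 30% v 15% | 2% v 5% | 31.40% v 19.25% | 12.15 | 35% |
| 30% v 15% | 2% v 10% | 31.40% v 23.50% | 7.90 | 17% |
| 40% v 20% | 0 v 0 | 40.0% v 20.0% | 20.0 | 70% |
| 40% v 20% | 1% v 3% | 40.6% v 22.4% | 18.2 | 60% |
| 40% v 20% | 2% v 5% | 41.2% v 24.0% | 17.2 | 55% |
| 40% v 20% | 2% v 10% | 41.2% v 28.0% | 13.2 | 35% |

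From a 15-point start, the loss runs from 1.85 points (12%) to 7.1 points (47%); from a 20-point start, from 1.8 points (9%) to 6.8 points (34%). The direction follows from Section 17. The size depends entirely on the assumed rates.

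**The case against.** The strongest reply is that all-cause ICU admission under intention to treat is a legitimate net outcome. It counts harm-driven admissions because they are part of what the dose does, just as the primary endpoint counts all deaths. One event may properly appear in both an efficacy and a safety summary, and no single analysis counts it twice. This stands, and it is why the all-cause endpoint should stay.

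Four stronger readings are tempting, and the documents do not support them.

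- *ICU admission defines the hyperglycemia event.* It is one of two alternatives, and in Section 4 only when it is to control hyperglycemia.
- *A metabolic side effect is scored as lack of respiratory efficacy.* No section calls ICU admission respiratory. Oxygen escalation, invasive ventilation and its duration, ECMO and tracheostomy are separate endpoints, and a glucose-only admission does not by itself meet any of them. A charge of bias holds only against a cause-specific target that the plan does not state.
- *The two can never be separated.* Applying the Section 4 definition already requires a judgement on why the patient was admitted, and the data come from the medical record, so chart review could recover much of it. The defect is that the plan does not list the reason for collection.
- *The overlap would turn a significant ICU result into a non-significant one.* Counts can be chosen to show this: with 71 per arm, 21 v 11 admissions gives p = 0.045 by uncorrected chi-squared, and adding 1 v 4 glucose-only admissions gives 22 v 15 and p = 0.18. But the counts are invented, and 21 v 11 gives p = 0.070 by Fisher's exact test, which Section 12 also allows. The contrast reflects the choice of counts and test.

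It is also fair to say that redefining the main ICU endpoint by a judged cause, with no blinding described, would bring in the same subjectivity for which the hyperglycemia endpoint is criticised. It could selectively remove events from the higher-dose arm. Finally, restricting the safety endpoint to clinically significant hyperglycemia is a legitimate severity threshold, so a laboratory measure belongs beside it and should not replace it.

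**Conclusion.** The concern holds as a limit on interpretation and on safety measurement. The overlap is real but partial, its expected direction is against the higher dose, and the plan lists neither a reason for ICU admission nor a cause-specific analysis. An absent or reduced ICU effect would be hard to explain. Separately, the hyperglycemia endpoint depends on care decisions and misses cases managed on the ward.

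The reach is limited to ICU admission, ICU length of stay and possibly hospital length of stay, none of which is powered, together with the hyperglycemia endpoint. The primary endpoint, its test and the sample size are untouched. The documents do not allow the size to be determined. The attenuation shown, from about a tenth to about a half of the assumed benefit, rests on assumed ICU rates and assumed rates of glucose-only admission, and would be negligible if such admissions were rare. These are inexpensive improvements and do not correct an invalid analysis.

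**What to change.** 1. Keep all-cause ICU admission and ICU length of stay as the stated secondary endpoints.
2. Add the primary reason for ICU admission to the Section 11 data list (respiratory or haemodynamic deterioration, glucose control, other). In Section 12, report ICU admission for reasons other than glucose control as a supplementary analysis.
3. Report the insulin-drip and ICU components of the hyperglycemia endpoint separately by arm, and make the wording in Sections 4 and 10 identical.
4. Add a supporting laboratory safety measure from glucose values already in the record, such as the highest glucose during treatment by arm, split by baseline diabetes.

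The cost is one extra data field, extraction of existing values and a few lines of wording; no new test or procedure for patients is involved. The downside is the judgement needed to assign a reason, especially for admissions with mixed causes and with no blinding described. Keeping the all-cause endpoint as the stated one covers that.
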